#### 4.1 Inclusion exclusion criteria

Inclusion criteria	Exclusion criteria

• Subject >18 years of age.

• Having new onset symptoms suggestive of acute respiratory infection (ARI within 7 days of seeking care: runny nose, nasal congestion, sore throat, cough, hoarse voice, softness of breath) with or without fever.

	

• Unable to provide informed consent.

• Undergoing end of life care.

• Immunocompromised or taking chemotherapy, oral steroids, or interferon.

• Receiving a live vaccine in the last 14 days.

• Taking antibiotics or antivirals in the last 14 days.

• Patients that have symptoms lasting more than 7 days.

**Table 2:** Inclusion and Exclusion criteria for the Aspire study.

Clinical assessment including the POC assay can also be offered to patients with any of the following conditions following NICE guidelines (see Appendix 1a for NICE guideline pathways, figures 3, 4, 5, 6):

[figure not shown]
- Acute otitis media
- Pharyngitis
- Common cold
- Acute rhinosinusitis
- Acute cough/bronchitis

Patients testing positive for bacterial infections can be prescribed appropriate antibiotics following NICE prescribing pathway for common infections (see Appendix 1a fig 7).

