### 4.0 Study Participants

The study population will be recruited from self-referred patients attending YCR and KHPC centres with a self-suspected acute respiratory infection (ARI). The study aims to collect a minimum of 140 participants using a pragmatic sampling regime. The feasibility study will

provide the data required to design and conduct a more detailed and statistically powered trial.

The ASPIRE study will not replace clinical judgement or expertise. Patient management actions will be based on clinical judgement independent of the POC assay results. The physician will only have access to this data after the patient has finished their consultation.

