## **6. Data collection**

The POC test result will be performed in a separate room after the consultation is over and the patient's treatment decided upon. The GP will be blinded to the study and presented an information sheet and consent form prior to the patient's consultation to agree upon these terms.

The POC assay outcome and the participant characteristics at presentation will be recorded on CRF 1. All patient identifiable data will remain at Keir Hardie and Ysbyty Cwm Rhondda Primary Care Centres. The following information will be collected:

Demographics: Age, Sex, Weight, Height

Clinical Findings, Arterial O2 Saturation, resting heart Rate, CRB, resting Respiratory Rate and (office) Blood Pressure (where available).

The CRF 1 will also record any additional tests the GP may have requested as per the standard treatment procedure such as sputum or PCT tests. CRF1 will record the final diagnosis.

CRF1 will include a tick-box to state whether the participant has agreed to participate in a follow-up call after 14 days of their initial appointment. Each participant will be asked if they would be able to conduct a short telephone call with the research student to discuss the

outcomes of the treatment. If consented, the participant will confirm this on a tick box on CRF 1 and will be asked to provide a suitable contact mode and time to call back on the follow up form. Follow up data will be recorded on CRF 2.

Participant's medical records will be reviewed at the Primary care Practice to collect data concerning follow up treatment after 14 days to determine whether patients returned for medical treatment post appointment. Patient medical records will also be used to determine the clinical judgment of the initial assessment i.e. where they prescribed antibiotics or not. The clinical judgement and course of treatment followed will then be compared to the course of treatment that would have been suggested by the POC dual marker immunoassay result.

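### Section 4.1 permits antibiotics after a positive bacterial test, which on its natural reading contradicts the rule in Sections 4.0 and 6 that the assay does not guide treatment

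*Protocol*

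**What the plan says.** Three parts of the protocol bear on whether the assay may influence treatment.

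- **Section 4.1 (Inclusion exclusion criteria).** Below the eligibility table, the text widens the offer of testing: "Clinical assessment including the POC assay can also be offered to patients with any of the following conditions following NICE guidelines". A list of conditions follows, and then: "Patients testing positive for bacterial infections can be prescribed appropriate antibiotics following NICE prescribing pathway for common infections". That sentence does not name the test. It points to Figure 7, captioned as a NICE overview of antimicrobial prescribing.
- **Section 4.0 (Study Participants).** "Patient management actions will be based on clinical judgement independent of the POC assay results". The next sentence sets when the result becomes available: "The physician will only have access to this data after the patient has finished their consultation".
- **Section 6 (Data collection).** The assay is "performed in a separate room after the consultation is over" and once treatment has been settled. It adds: "The GP will be blinded to the study".

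Section 6 also defines what is compared. First: "Patient medical records will also be used to determine the clinical judgment of the initial assessment i.e. where they prescribed antibiotics or not". Then: "The clinical judgement and course of treatment followed will then be compared to the course of treatment that would have been suggested" by the assay. Treatment found in the records after 14 days is a separate item, collected to see whether patients came back. Section 1.1 (Study Setting) says the assay results will be compared with clinical outcomes and with the treatment pathway directed by the physician. The sources it gives are medical records and contact with the patient from 14 days after the visit.

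**The concern.** The study is described as observational. Its value rests on the GP's decision being made without the assay, so that the decision can be set against what the assay would have advised. A sentence that lets a positive result lead to a prescription gives sites a second instruction that does not fit the first.

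Two things would be at stake if a site acted on it. First, some participants would be treated on the assay, so their 14-day outcomes would no longer reflect management without it. The direction of that effect cannot be told from the protocol. Second, an antibiotic prompted by the assay might be recorded as part of the treatment that the assay is compared with, and the assay would then partly agree with itself. The data are meant to inform the design of a larger, powered trial, so either fault would carry forward.

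**Working it through.** The protocol gives no figure on this point, so there is none to reproduce. The check is a comparison of texts, followed by a bound in symbols.

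**Step 1: which test does Section 4.1 mean?** The assay is the only test named there, in the sentence that leads into the list of conditions. Sputum and PCT tests appear only in Section 6, as extras the GP may request. Future interventional use appears only in the caption of Figure 2, whereas the Section 4.1 sentence cites Figure 7. The assay is therefore the natural reading, though not the only possible one.

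**Step 2: do the instructions conflict on that reading?**

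| Question | Section 4.1 | Sections 4.0 and 6 |
|---|---|---|
| May the assay result lead to a prescription? | Yes, if bacterial | No; management is independent of it |
| When is treatment decided? | After a positive test | Before the test is run |
| What does the GP know? | The result, by implication | Blinded (6); no access until the consultation ends (4.0) |

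They conflict on each row.

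**Step 3: could a GP act on Section 4.1?** Yes. Section 4.0 delays access to the result only until the consultation ends. Section 6 gives no end point for the blinding and no rule for handling the result afterwards.

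**Step 4: where would such a prescription enter the data?**

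- *Clinical judgement.* Section 6 ties this to the initial assessment and to whether antibiotics were prescribed then. A later prescription does not belong in it, so this part is protected.
- *Treatment course.* Section 6 names this beside the clinical judgement and gives it no end date. It is exposed only if read beyond the initial assessment.
- *14-day outcomes.* These are exposed, because a participant treated on the result may have a different course or be less or more likely to return.

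**Step 5: bound on the treatment comparison.** Suppose later changes were wrongly counted as the GP's treatment.

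- Let q be the share of participants whose assay is bacterial and who were untreated at the consultation. Let r be the fraction of these started on an antibiotic because of the result. Recorded discordance in this group falls from q to q(1 − r). The shift is qr, between 0 (r = 0) and q (r = 1).
- Section 4.1 permits starting only. Access after the consultation could also lead a GP to stop an antibiotic on a viral result. Let p be the share given an antibiotic whose assay is viral, and s the fraction stopped. If stops were counted in the same way, discordance there falls from p to p(1 − s), a shift of ps, between 0 and p.

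Both shifts raise apparent agreement. The protocol gives none of q, r, p or s, so no number follows. If the comparison uses only the initial decision, both shifts are 0.

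**The case against.** The strongest reply is that the comparison is already anchored. The assay comes after treatment is settled. The item taken from the records is the judgement at the initial assessment, and the next sentence continues from it. The comparison is with what the assay *would have* suggested, which presupposes that the result did not direct treatment. Treatment after 14 days is a separate item with its own purpose. On this view, circular agreement needs three things together: the Section 4.1 sentence means the assay, the GP acts on it despite Section 4.0, and the analyst counts the later antibiotic as the initial decision despite Section 6.

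Most of that stands. A reader might infer that the agreement between GP and assay is circular by design. The documents do not support that; only the loosely worded treatment course and the 14-day outcomes are exposed. A reader might also infer that the bias can touch only untreated patients with a bacterial result. That follows from the Section 4.1 permission alone and not from access to the result in general, as Step 5 shows.

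It can also be said that the sentence may mean routine tests or future use, and that time cut-offs for analysis variables are commonly left to an analysis plan. The first is possible, but then the sentence should say so. The second is fair as regards the cut-off, but an analysis plan cannot withdraw a permission to prescribe that the protocol gives to sites. Finally, the case report forms are not shown, so nobody can say that dates of later prescriptions go uncaptured.

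**Conclusion.** The point holds as a contradiction between instructions in the protocol. On its natural reading, Section 4.1 allows treatment on the assay result, while Sections 4.0 and 6 exclude it. Release of the result after the consultation makes it practicable to act on the permission.

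The consequence for the data is possible, not certain. The 14-day outcomes could be affected, in an unknown direction. The treatment comparison could be affected, towards agreement, only if the treatment course is read past the initial assessment. The size cannot be derived. All of this assumes that the test meant in Section 4.1 is the assay and that some GPs would act on it. It is worth fixing before recruitment, because it concerns what sites are told to do and the correction is small.

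**What to change.** 1. **Section 4.1.** Delete the sentence, or state that it refers to routine tests or to possible future use. Add that no treatment is started on the assay result within the study.
2. **Sections 1.1 and 6.** State that the treatment comparator is the prescribing decision made at the consultation, before the finger-prick. This extends to the treatment course the anchor that Section 6 already gives to the clinical judgement.
3. **Follow-up.** Report any antibiotic started or stopped later as follow-up and not as the GP's initial treatment. Check that the existing forms capture the date of such changes; add a field only if they do not.

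The cost is a few sentences in three sections and a check of the forms. No extra patients or visits are needed, and the physician's access to the result after the consultation need not be delayed.

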### 5. Recruitment

Patients who have contacted their local Primary Care centre will be triaged for study inclusion by the receptionist when presenting with ARI symptoms and given an invitation letter and study pack (containing the Participant Information Sheet and Consent form).

Patients will be able to read through the study pack whilst waiting for their consultation and if required, additional time will be provided during the appointment.

#### **ASPIRE Study Patient Pathway**

\*Data Collection : 1= Quantitative & qualitative data from POC test systems, 2= Patient clinical records, 3= Telephone follow up.

^ Study Pack : Participant Information Sheet and Consent form.

**Figure 1: ASPIRE Study patient pathway.**

Once the GP has completed the routine consultation, the patient will be invited by their GP to partake in the study. Once consent has been obtained by the GP, the participant will be invited to take the POC test. A finger prick blood sample of 5 microliters will then be obtained by [name] and used for the POC test. The GP and nursing staff will be available in the event the patient feels anxious or stressed at any point in the sampling.

## **6. Data collection**

The POC test result will be performed in a separate room after the consultation is over and the patient's treatment decided upon. The GP will be blinded to the study and presented an information sheet and consent form prior to the patient's consultation to agree upon these terms.

The POC assay outcome and the participant characteristics at presentation will be recorded on CRF 1. All patient identifiable data will remain at Keir Hardie and Ysbyty Cwm Rhondda Primary Care Centres. The following information will be collected:

Demographics: Age, Sex, Weight, Height

Clinical Findings, Arterial O2 Saturation, resting heart Rate, CRB, resting Respiratory Rate and (office) Blood Pressure (where available).

The CRF 1 will also record any additional tests the GP may have requested as per the standard treatment procedure such as sputum or PCT tests. CRF1 will record the final diagnosis.

CRF1 will include a tick-box to state whether the participant has agreed to participate in a follow-up call after 14 days of their initial appointment. Each participant will be asked if they would be able to conduct a short telephone call with the research student to discuss the

outcomes of the treatment. If consented, the participant will confirm this on a tick box on CRF 1 and will be asked to provide a suitable contact mode and time to call back on the follow up form. Follow up data will be recorded on CRF 2.

Participant's medical records will be reviewed at the Primary care Practice to collect data concerning follow up treatment after 14 days to determine whether patients returned for medical treatment post appointment. Patient medical records will also be used to determine the clinical judgment of the initial assessment i.e. where they prescribed antibiotics or not. The clinical judgement and course of treatment followed will then be compared to the course of treatment that would have been suggested by the POC dual marker immunoassay result.

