## 2. Introduction

### 2.1 Lay Summary

Antibiotic stewardship is fast becoming an essential measure to improve antibiotic prescribing by clinicians. Antibiotic stewardship not only presents a cost-effective strategy for the NHS but addressed the issue of antimicrobial resistance (AMR) and protects patients from harm caused by unnecessary antibiotic use.

The economic costs of antibiotic resistance are largely unknown, but it is anticipated that with an increased number of cases, effects to the economy could be severe. Infections and infectious diseases cost England & Wales an estimated £30 billion a year, with many cases of acute respiratory infections (Chaplin, 2017). POC diagnostic tests in a clinical setting could give clinicians the ability to distinguish between microbial and viral infections, providing a more informed decision to antibiotic prescribing.

The purpose of this study is to safely distinguish between bacterial or viral respiratory infections in a primary care setting using "point of care" (POC) testing to provide a retrospective insight as to whether clinical assessment of an acute respiratory infection (ARI) is justified. Upon clinical assessment, the current clinical practice prescribes antibiotics based on symptoms reported by the patient and a subjective review by the GP. This results in antibiotics being prescribed from an informed decision made by the clinician, based only from patient symptoms. The use of a dual marker immunoassay could guide informed decisions based on qualitative data and degree of infection using POC testing in Primary Care.

The POC assay uses a dual marker immunoassay to differentiate between a viral and bacterial infection. C-reactive protein (CRP) is raised in the blood stream in response to inflammation. CRP can be elevated in viral infections, but generally the rise is to higher levels in bacterial infections, especially severe bacterial infections. Another blood protein, the MxA protein, is selectively increased in people with viral infections and therefore has the potential to greatly enhance the rapid distinction between viral and bacterial respiratory infections.

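### Masking is one-way: the GP is shielded from the assay result, but nothing keeps the assay reader unaware of the GP's diagnosis or prescription

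*Protocol*

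**What the plan says.** Protocol section 6 (Data collection) sets the order of events: "The POC test result will be performed in a separate room after the consultation is over and the patient's treatment decided upon".

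Masking is stated for the GP only. Section 6 says "The GP will be blinded to the study and presented an information sheet and consent form prior to the patient's consultation", and section 4.0 (Study Participants) adds that "The physician will only have access to this data after the patient has finished their consultation".

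On recording, section 6 says "The POC assay outcome and the participant characteristics at presentation will be recorded on CRF 1". The same form takes clinical findings and any tests that the GP requested, and "CRF1 will record the final diagnosis". Neither the author of that diagnosis nor its time of entry is given.

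The prescribing decision has a different source: "Patient medical records will also be used to determine the clinical judgment of the initial assessment i.e. where they prescribed antibiotics or not".

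The two are then set against each other: "The clinical judgement and course of treatment followed will then be compared to the course of treatment that would have been suggested by the POC" assay result.

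On the output, section 2.1 (Lay Summary) says "The use of a dual marker immunoassay could guide informed decisions based on qualitative data and degree of infection using POC testing in Primary Care". Section 2.2 also calls the output qualitative. The key to the patient pathway in section 5 lists quantitative as well as qualitative data from the test systems, and section 7 refers to quantitative data from the assay. No section gives a cut-off, a reading rule, or a procedure for an unclear result.

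**The concern.** A comparison of two judgements on the same patient is informative only if each is made without knowledge of the other. The protocol secures this for the GP and is silent for the assay.

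The participant reaches the test from a finished consultation and will usually know whether antibiotics were prescribed. If the reader learns this, or sees a diagnosis already on CRF 1, a result that needs any judgement can drift towards the GP's decision or away from it.

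At stake is the agreement between the treatment given and the treatment that the assay would have suggested. Section 2.1 describes the purpose as a retrospective look at whether the clinical assessment was justified, and section 4.0 says the data will serve the design of a powered trial. Bias of this kind would carry forward. It does not shrink with more participants and cannot be removed once the data are collected.

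**Working it through.** The protocol states no figure for agreement or reader error, so there is nothing to reproduce. The check is first a reading of the text, then an illustration of scale.

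**Direction of masking**

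| Direction | Safeguard in the protocol |
|---|---|
| Assay result to GP's treatment decision | Yes: assay run after the decision, in a separate room; result withheld until the consultation ends (sections 4.0 and 6) |
| GP's diagnosis or prescription to assay reading | None found in sections 4 to 8 or 11 |

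**Routes by which the reader could learn the GP's view**

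1. The participant. Sampling follows the consultation (section 5), so the prescription is normally known to the person being tested.
2. CRF 1. It holds both the assay outcome and the final diagnosis, with no stated order of entry.
3. The separate room parts the reader from the GP, but not from the participant or the form.

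Who reads the test is not stated apart from who takes the sample, and section 6 does not say who completes CRF 1.

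**Illustration 1: discordant readings moved to match the GP.** All rates are assumptions; the protocol gives none. Let g be the share prescribed antibiotics, and let the assay read bacterial in 40% of those prescribed and 20% of those not.

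- Discordance = g × (1 − 0.40) + (1 − g) × 0.20, and agreement = 1 − discordance.
- g = 0.5: discordance = 0.30 + 0.10 = 0.40, agreement 60.0%, kappa 0.20.
- g = 0.3: discordance = 0.18 + 0.14 = 0.32, agreement 68.0%, kappa 0.21.
- If a share x of discordant readings shifts to match the GP, agreement rises by x × discordance.

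| x | Agreement (kappa), g = 0.5 | Agreement (kappa), g = 0.3 |
|---|---|---|
| 0 | 60.0% (0.20) | 68.0% (0.21) |
| 5% | 62.0% (0.24) | 69.6% (0.25) |
| 10% | 64.0% (0.28) | 71.2% (0.29) |
| 20% | 68.0% (0.36) | 74.4% (0.37) |

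**Sampling error for scale**, at the planned minimum of 140 (section 4.0): the 95% half-width is 1.96 × √(p(1 − p)/140). For p = 0.60 it is 8.1 points. Over p = 0.50 to 0.80 it runs from 8.3 down to 6.6 points.

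**Illustration 2: worst case.** Assume that 5% to 15% of readings are borderline, that they would split evenly if read without knowledge of the GP's decision, and that all instead follow the GP. Then 0.05 × 140 = 7 and 0.15 × 140 = 21 readings are affected. Half of these, 3.5 to 10.5, change from discordant to concordant, which is 2.5 to 7.5 percentage points of 140. If all ran against the GP instead, the sign would reverse. The protocol supports neither the borderline share nor the complete drift.

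**The case against.** The strongest reply is that the mechanism is not documented. No section describes a borderline result, a reading by eye or a graded scale. The lay-summary phrase about degree of infection concerns how the assay might guide decisions, not how a result is read, and sections 5 and 7 mention quantitative data. If an instrument or a fixed rule gives the result, the bias largely disappears. This stands, and it is why no size can be claimed. It does not supply the missing safeguard, because the protocol does not say that the reading is objective.

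Three stronger readings are tempting, and the text does not support them.

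- **A reader might infer that testing after the treatment decision is the fault.** It is a strength: it keeps the GP's decision independent of the assay.
- **A reader might infer that CRF 1 shows the assay reader the GP's decision.** The final diagnosis is not attributed to the GP, its time of entry is open, the prescription comes from the medical records, and the person completing the form is not named. The shared form is a possible route to unmasking and not a demonstrated one.
- **A reader might infer that agreement will be wrong by 2.5 to 7.5 points.** That range is a worst case on assumed inputs. If only a fifth of the assumed excess drifted, it would be 0.5 to 1.5 points (0.2 × 2.5 and 0.2 × 7.5).

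It can also be said that entry order belongs in the CRF or a working instruction, which are not shown. The page layout may well be settled there. Who is masked to what is protocol content, and section 6 already deals with it in one direction.

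**Conclusion.** The point holds as a gap in masking and not as a demonstrated bias. The protocol shields the GP from the assay but does not shield the assay reading from the GP's decision, although the two are then compared. Agreement could be biased in either direction to the extent that reading the result involves judgement.

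The size is unknown. On the assumed rates above, a 5% shift of discordant readings adds about 2 points, well inside sampling error at 140 participants. A 20% shift adds about 6 to 8 points, similar to sampling error. These figures show scale only.

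The conclusion rests on two assumptions: that participants usually know their prescription, and that the reading is not fully automatic. For an uncontrolled feasibility study this is a worthwhile and inexpensive improvement, to be made before data collection because it cannot be made afterwards.

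**What to change.** Keep the assay after the treatment decision. Add to section 6:

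- The assay operator is not told the GP's diagnosis or prescription, and asks the participant not to disclose it.
- The result is read by a fixed, stated rule, and the protocol says whether the reading is by eye or by instrument.
- The result is entered, with time and initials, on a separate assay page before the operator sees any diagnosis, prescription or medical record.
- Later changes to that entry are made only as dated, traceable corrections, so that a genuine recording error can still be put right.

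It would also help to state who enters the final diagnosis on CRF 1 and when. The GP may see the assay result after the consultation, so a diagnosis entered late could be influenced by it.

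The cost is one added instruction and a separate assay page, with no extra staff, visit or sample. Some participants may still disclose their prescription, so the protection will be good but not complete.

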### **1.1 Study Setting**

The ASPIRE study is an uncontrolled observational feasibility study, and a collaboration between the University of South Wales and Cwm Taf Morgannwg University Health Board (CTMUHB). The study is based at Ysbyty Cwm Rhondda (YCR) and Keir Hardie

Primary Care (KHPC) centres, where participant recruitment will take place. Study participants will be invited to provide capillary blood samples (via finger prick sampling) for testing. The principal investigators are [name] at YCR and [name] at KHPC. Upon clinical assessment, and after provision of consent, participants will undergo an ARI (acute respiratory infection) POC assay. This is a dual marker immunoassay designed to detect raised levels of C-reactive protein and MxA in capillary blood. The assay uses the sensitivity of CRP and specify of MxA to aid in the differentiation of ARI's in Primary Care.

The POC assay results will be compared to the participants' clinical outcomes and the physician directed treatment pathway via reviewing medical records and by contacting the patient from 14 days after their visit.

The study is funded by a KESS award.

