### 3.0 Study Aims and Objectives

A Primary care administered POC dual marker immunoassay utilising new technologies allowing on-site “in-house” diagnosis of ARI's may reduce unnecessary antibiotic prescribing by defining the bacterial or viral source of the infection. The POC assay could be used to guide GP's patient treatment and management decisions.

The primary objective of the study is to determine whether the POC assay is useful in aiding clinicians in the decision to prescribe antibiotics (Table 1).

Primary aims	Secondary aims

 
• Use a POC assay to distinguish between bacterial and viral infection in the Primary Care setting.
 
• To assess the feasibility of using POCT to support clinician decision making in prescribing antibiotics.
 
	
 
• Produce data to evaluate usefulness of the POC assay.
 
• Compare POC assay use to other POC assays used in Primary Care.
 

**Table 1:** Primary & Secondary Study aims.

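### No reference for infection cause covers every participant and is independent of both GP and assay, so conclusions should be limited to feasibility and agreement

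*Protocol*

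**What the plan says.** Section 2.1 of the protocol gives the purpose in two parts: "The purpose of this study is to safely distinguish between bacterial or viral respiratory infections in a primary care setting", and "to provide a retrospective insight as to whether clinical assessment of an acute respiratory infection (ARI) is justified". In Section 3.0 the first primary aim is "Use a POC assay to distinguish between bacterial and viral infection in the Primary Care setting"; the second is the feasibility of point-of-care testing to support prescribing decisions.

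Section 1.1 labels the study uncontrolled, observational and a feasibility study. It sets assay results against "clinical outcomes and the physician directed treatment pathway via reviewing medical records" and patient contact from 14 days.

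Section 6 fixes what is collected:

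- **Main comparison.** "The clinical judgement and course of treatment followed will then be compared to the course of treatment that would have been suggested by the POC" dual-marker result. Clinical judgement is read from the records as antibiotics prescribed or not.
- **Other tests.** CRF 1 records "any additional tests the GP may have requested as per the standard treatment procedure".
- **Diagnosis.** "CRF1 will record the final diagnosis". The visible text states no independent source for it.
- **Follow-up.** Records are reviewed after 14 days "to determine whether patients returned for medical treatment post appointment". A telephone call about treatment outcomes takes place only if the participant agrees.

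Sections 4.0 and 6 say that treatment is decided before, and without, the assay result. Section 7 says that assay data will be analysed alongside medical records and clinical outcome.

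**The concern.** To judge whether an assessment was justified, or whether an assay classified correctly, one needs a standard outside both. The central comparison here sets one fallible classification against another, and the protocol itself treats both as fallible. Section 2.2 says that antibiotics are often prescribed when infection is probably viral, so a prescription is not a statement of cause. The same section cites assay agreement of 92% and 84-87%, which is not perfect.

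Under the present wording, a disagreement could be reported as unjustified prescribing, or as the assay being right, when the data support neither. Section 4.0 says that the study will supply data for designing a powered trial, so such a reading could be carried forward. An analysis plan cannot repair this later, because it cannot supply reference data that were never collected.

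**Working it through.** **1. Is there a usable reference?** The candidates in Sections 1.1, 6 and 7, taken in turn:

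- *GP's prescription.* Available for all participants, but it is one of the two things compared.
- *GP-requested tests.* Independent of the assay result, but available only where the GP chose to test.
- *CRF 1 final diagnosis.* No independent source is stated, and the form also carries the assay outcome. It cannot be assumed independent of either side.
- *Return for treatment after 14 days.* Follows the GP's own treatment and does not identify cause.
- *Telephone call.* Optional; covers treatment outcomes, not cause.

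None covers all participants, is independent of both GP and assay, and identifies cause.

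**2. Is there a plan figure to reproduce?** The only design figure is the minimum of 140 participants in Section 4.0. It is called pragmatic and has no stated inputs, so there is nothing to reproduce.

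**3. Illustration: disagreement when the GP is never wrong.** Inputs: sensitivity (Se) 80% and specificity (Sp) 90%, the floor cited in Section 2.1; bacterial share π of 10% to 30% (assumed); a prescription counted as a bacterial call (assumed).

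Disagreement = (1 − Se)·π + (1 − Sp)·(1 − π)

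- π = 0.10: 0.20 × 0.10 + 0.10 × 0.90 = 0.110, or 15.4 of 140
- π = 0.20: 0.20 × 0.20 + 0.10 × 0.80 = 0.120, or 16.8 of 140
- π = 0.30: 0.20 × 0.30 + 0.10 × 0.70 = 0.130, or 18.2 of 140

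With an assumed 90%/95%, the results are 0.055, 0.060 and 0.065, or 7.7, 8.4 and 9.1 of 140.

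**4. Illustration: one table, three readings.** Take an invented table of 140: 22 both bacterial, 6 GP only, 11 assay only, 101 neither.

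- GP always right: assay Se = 22/28 = 79%, Sp = 101/112 = 90%.
- Assay always right: GP Se = 22/33 = 67%, Sp = 101/107 = 94%.
- Both imperfect, errors independent given cause: π = 0.2208, GP 0.80/0.97, assay 0.8828/0.9476. Both bacterial = 140 × (0.2208 × 0.80 × 0.8828 + 0.7792 × 0.03 × 0.0524) = 22.0. The other cells come to 6.0, 11.0 and 101.0 in the same way.

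A single pooled table has 3 free proportions. The unknowns number 5: the bacterial share, two sensitivities and two specificities. More participants would not resolve this.

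**5. Illustration: the GP used as reference.** Keep the assay at a true 80%/90% and errors independent given cause. Apparent sensitivity is the share of GP-bacterial participants who are also assay-bacterial.

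- π = 0.10, GP 60%/60%: (0.1 × 0.8 × 0.6 + 0.9 × 0.1 × 0.4)/(0.1 × 0.6 + 0.9 × 0.4) = 0.084/0.42 = 0.20
- π = 0.40, GP 90%/90%: (0.4 × 0.8 × 0.9 + 0.6 × 0.1 × 0.1)/(0.4 × 0.9 + 0.6 × 0.1) = 0.294/0.42 = 0.70

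**6. What can be estimated.** Percent agreement p needs no reference for cause. With 140 complete pairs the approximate 95% half-width is 1.96·√(p(1 − p)/140): 8.3 percentage points at p = 0.5 and 5.0 at p = 0.9.

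**The case against.** The strongest reply is that the protocol already claims little. It calls itself a feasibility study, defers to a later powered trial, has feasibility as a primary aim, and promises no estimate of sensitivity or specificity. The first aim can be read as simply deploying the assay. The phrase 'is justified' stands in a lay summary, softened to a retrospective insight, and is not an endpoint. Much of this stands. A reader might infer that the study is invalid, or that it fails a promised accuracy analysis. The documents support neither: if the first aim means deployment, it can be met. What remains is that 'is justified' is stated as part of the study's purpose and claims more than the planned data can show.

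Second, GP blinding and follow-up do add information. Blinding makes the prescribing decision independent of the assay result, and follow-up bears on how patients fared. Neither supplies the cause of infection.

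Third, the count of 5 unknowns against 3 proportions applies to one pooled table. Two centres would give 6 proportions for 6 unknowns, provided that the bacterial share differs between centres, accuracy is the same in both, and errors are independent given cause. The protocol claims none of these, so this is no rescue, but the count is not an absolute barrier.

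Fourth, agreement statistics, confidence intervals and the mapping from assay result to suggested treatment may stand in an analysis plan that is not shown. Their absence here is no part of this point. Nor is the unstated authorship of the final diagnosis a fault in itself; it matters only because that diagnosis cannot be taken as an independent reference.

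**Conclusion.** The point holds in a limited form. The planned data cannot show whether the GP's assessment was justified. They also cannot show that the assay classifies correctly, if Section 2.1 and the first primary aim are read as accuracy claims. Feasibility and a description of GP-assay agreement are attainable.

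This conclusion rests on what is collected, not on any assumed number. The sizes are illustrations: 15 to 18 disagreements in 140 with a GP who is never wrong, or about 8 to 9 with a better assay. A reader might take these, or the 140-patient table, as forecasts for this study. They are not: the 10% to 30% bacterial share and the table are assumptions, and coding a prescription as a bacterial call is a simplification that the protocol's own background argues against.

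It is also tempting to say that the wording decides what the later trial will assume. Section 4.0 says only that the study will provide data for that trial's design, so this is a risk and not an established consequence.

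**What to change.** Change the wording in three places:

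- **Section 2.1.** Replace 'is justified' with 'agrees with the assay result', and reword 'safely distinguish' so that it describes use of the assay.
- **Section 3.0.** Word the first primary aim as describing assay results and their agreement with the GP's prescribing decision.
- **Section 7.** State that GP-assay disagreement will not be interpreted as an error by either side, that conclusions are limited to feasibility and agreement, and that participants with GP-requested tests are a selected subset.

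No extra tests, visits or participants are needed. The cost is an amendment that touches a primary aim, and a less ambitious claim. The choice of agreement statistics can be left to the analysis plan.
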